### Exclusion Criteria (note that we are no longer excluding Veterans with specific health issues)

- Non-Veterans
- A documented current history of active psychosis or other cognitive issues via ICD-10 codes
- Has participated in  $\geq 4$  MOVE! sessions in the past year
- Pregnancy

- PCP stating that Veteran should not participate
- Self-reported inability to read at a 5th grade level due to literacy level or vision problems

With an expected 20% participation rate (based on pilot data) and a 75% retention rate (based on rates from another VA study and other technology-based interventions), we will need to screen 2,615 Veterans with overweight/obesity to enroll a baseline sample of up to 520 Veterans and end with 392 Veterans completing the study. With a screening rate of approximately 30-35 Veterans per week (6 women, 24 men), we will be able to recruit our target population by the middle of Year 3 (recruitment will start the first quarter of Year 2).

Study Arms/Randomization – Under the direction of the study statistician, the PACT teams will be randomized at the provider level using a random number generator to either the PAL Intervention or Enhanced Usual Care intervention arms.

- *PAL Intervention group:* Participants will arrive and complete consenting materials, a Baseline Survey, and the GEM tool. They will then have a brief break if needed. After the break, they will work collaboratively with the Health Coach using tool-generated materials to modify their goals into SMART goals (specific, measurable, attainable relevant, and timely). The patient will then receive materials containing an individualized report with a summary of their personalized advice, initial goals, and barriers and facilitators to weight loss. They will also receive a packet of MOVE! handouts tailored to their questionnaire responses and schedule 10-12 follow-up health coaching phone calls during the next 12 months of intervention. The Health Coach will also inform the patient of the resources available to them at the VA (e.g. MOVE, TeleMOVE!) that can assist them in achieving their goals.

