Sample Size and Power Analysis – We base our sample size on within-person weight change at Baseline and 12 months in each arm. We assume an interclass correlation coefficient (ICC) of 0.05 for Veterans within each PCP and an ICC of 0.01 for PCPs within each PACT team. Assuming that at the end of the study we have 5 teams in each intervention arm and recruit and obtain baseline data for 52 Veterans per PACT team (392 Veterans total at 12 months), we will have sufficient power to detect a 2.2kg (SD=6.0kg) difference in weight between the intervention and non-intervention arms. If we do not have PACT attrition (5 PACT teams per arm), then we will have additional power. This amount of weight loss is consistent with findings from the ASPIRE VA study and a systematic review of technology-assisted weight loss interventions in primary care. We will also have the power to detect our hypothesized difference of 15% of PAL Intervention Veterans achieving 5% weight loss (clinically significant—as little as 5% weight loss can improve cardiovascular risk), 85% assuming 12% of intervention arm Veterans achieve this amount of weight loss. We will be able to detect 2.9cm change in waist circumference.

If we assume the missing rate at 12 months is 15%, then we will have 44 evaluable Veterans per team. We assume an interclass correlation coefficient (ICC) of 0.03-0.04 for Veterans within each PACT team and an ICC of 0.01 for PCPs within each team. If the ICC of Veterans within each PACT team is 0.03, the power is 85% to detect a 2.2kg (SD=6.0kg) difference in weight between the intervention and intervention arms; the power is 87% to detect a 2.9cm (SD=7.7cm) difference in waist circumference. This amount of weight loss and waist circumference change is consistent with findings from the ASPIRE VA study and a systematic review of technology-assisted weight loss interventions in primary care. In addition, the power is 91% to detect our hypothesized difference between 25% Veterans in the intervention arm and 10% of Veterans in the control arm achieving 5% weight loss (clinically significant). If the ICC of Veterans within each PACT is 0.04, the powers are 81%, 83%, and 87% to detect the same effect sizes of weight loss, waist circumference, and proportion of 5% weight loss, respectively.

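### All six stated powers assume 15% missing at 12 months, while enrolment is planned on 75% retention; at the planned retention each power is roughly 1.5 to 3 points lower

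*Combined protocol and SAP*

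**What the plan says.** The recruitment paragraph that follows the Veteran exclusion criteria plans on "a 75% retention rate (based on rates from another VA study and other technology-based interventions" and sets out "to enroll a baseline sample of up to 520 Veterans and end with 392 Veterans completing the study".

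The first paragraph of Sample Size and Power Analysis (under Data Analysis, and repeated after Aim 3 in Statistical and Data Analysis) is consistent with this. It supposes that "at the end of the study we have 5 teams in each intervention arm", that the study will "recruit and obtain baseline data for 52 Veterans per PACT team", and that there will be "392 Veterans total at 12 months". For weight it calls the power sufficient but gives no figure.

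The second paragraph, which appears only after Aim 3, changes the retention: "If we assume the missing rate at 12 months is 15%, then we will have 44 evaluable Veterans per team". Its clustering assumption reads "We assume an interclass correlation coefficient (ICC) of 0.03-0.04 for Veterans within each PACT team and an ICC of 0.01 for PCPs within each team". At ICC 0.03, "the power is 85% to detect a 2.2kg (SD=6.0kg) difference in weight", with 87% for waist (2.9 cm, SD 7.7 cm) and 91% for 5% weight loss (25% against 10%). At ICC 0.04 the three powers are 81%, 83% and 87%.

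**The concern.** Both paragraphs start from 52 Veterans per team in ten teams, but they lose different shares of them. The first ends with 392 Veterans and the second with 440. The second gives no reason for the better rate. The rate that carries a source, and that sets the screening and enrolment targets, is 75%.

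A reader looking for the trial's power will take the six figures in the second paragraph, because they are the only clear numerical powers in the plan. They count 440 - 392 = 48 Veterans whom the plan does not expect to have at 12 months. At stake is whether the quoted power for the primary outcome, weight loss at 12 months, matches the trial as planned.

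**Working it through.** **Retention inputs.** 52 x 0.85 = 44.2, so 44 per team and 440 in ten teams. 52 x 0.75 = 39 per team. 392 / 520 = 75.4%, or 39.2 per team.

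**Assumptions not in the documents.** Two-sided alpha 0.05, normal approximation, equal cluster sizes.

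**Formulas.** With C clusters per arm, m evaluable Veterans per cluster and intracluster correlation r:
- design effect DE = 1 + (m - 1)r, and effective n per arm = C x m / DE
- means: power = Phi[(difference / SD) x sqrt(n_eff / 2) - 1.96]
- proportions (unpooled variance): power = Phi[(0.25 - 0.10) / sqrt((0.25 x 0.75 + 0.10 x 0.90) / n_eff) - 1.96]

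**Step 1: reproduce the stated figures.** Ten clusters of 22 per arm (220 Veterans) come close to all six. This structure is inferred from the fit; the plan does not state it, and it leaves out the 0.01 ICC for PCPs within team. For weight at ICC 0.04: DE = 1 + 21 x 0.04 = 1.84; n_eff = 220 / 1.84 = 119.6; (2.2 / 6.0) x sqrt(59.8) - 1.96 = 0.875; power 80.9% against the stated 81%.

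**Step 2: change retention only.** 392 completers give 196 per arm, or 19.6 per cluster. For weight at ICC 0.04: DE = 1 + 18.6 x 0.04 = 1.744; n_eff = 196 / 1.744 = 112.4; power 78.5%.

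| Outcome | ICC | Stated | 220 per arm | 196 per arm |
|---|---|---|---|---|
| Weight | 0.03 | 85% | 85.4% | 82.8% |
| Weight | 0.04 | 81% | 80.9% | 78.5% |
| Waist | 0.03 | 87% | 87.2% | 84.8% |
| Waist | 0.04 | 83% | 82.9% | 80.6% |
| 5% loss | 0.03 | 91% | 91.1% | 89.1% |
| 5% loss | 0.04 | 87% | 87.6% | 85.5% |

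The fit is not exact in the last row: 87.6% against the stated 87%.

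**Step 3: vary the cluster structure.**
- *Nested, with the 0.01 ICC included.* With k PCPs per team and m Veterans per team, DE = 1 + (m/k - 1)r + (m/k)(k - 1) x 0.01. At k = 3, moving from 44 to 39 per team takes weight from 83.8% to 81.2% (ICC 0.03) and from 80.9% to 78.4% (ICC 0.04).
- *Starting from the stated powers.* The stated 81% for weight implies n_eff = 119.8 per arm. Scaling it by the ratio of effective sizes at 39 and 44 per team gives 79.3% for k = 1 and 78.2% for k = 5. Across all six powers the loss is 1.5 to 1.9 points for k = 1 and 1.9 to 2.8 points for k = 2 to 5.
- *Seventeen clusters in all (8.5 per arm), the number of PACTs in Project Methods.* Weight at ICC 0.04 goes from 77.7% to 75.4%.
- *Literal reading: five teams per arm, ICC at team level.* At 44 per team, DE = 1 + 43 x 0.03 = 2.29 and n_eff = 220 / 2.29 = 96.1, so weight power is 71.9%; at ICC 0.04 it is 64.5%. At 39.2 per team these become 69.8% and 62.7%. The stated powers are not reproduced, but retention still costs about 2 points.

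The retention cost is therefore stable across structures, while the level of power is not.

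**The case against.** The second paragraph is worded as a conditional, and 15% of 52 is worked out correctly. It also uses other ICCs and other responder rates than the first paragraph, so it can be read as a separate scenario. That much stands: this is a conflict between inputs, and the powers are too high only relative to the plan's own retention. A reader might infer an arithmetic error, which the text does not show. But the conditional does not remove the problem. The 15% is not labelled optimistic, and no matching weight power is given at 75%. The first paragraph does contain an 85%, but in a garbled sentence about 5% weight loss.

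A reader might also infer that the trial misses its own power target. The documents set no such target; 80% is a convention, and at ICC 0.03 weight stays near 83% under the ten-cluster structure.

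Nor do the documents support 83% and 78% as the correct replacements. Ten clusters per arm appears nowhere in the plan, which speaks of 17 PACTs randomised at provider level, and the text attaches the 0.03-0.04 ICC to Veterans within teams.

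Finally, the Aim 1 mixed model uses all visits, so a Veteran who misses only the 12-month weight can still contribute. Counting completers may therefore somewhat overstate the loss for that model. The plan's own power statements, however, count evaluable Veterans at 12 months.

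**Conclusion.** The inconsistency is real and sits in the current text. All six powers rest on an unexplained 15% missing rate (440 Veterans), while enrolment and the first power paragraph rest on 75% retention (392). Correcting retention alone lowers each power by roughly 1.5 to 3 points and takes the stated 81% for weight at ICC 0.04 to about 78-79%. This assumes two-sided alpha 0.05 and a normal approximation.

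The replacement values themselves cannot be fixed from the documents. Weight power at 392 completers is about 83% and 78% (ICC 0.03 and 0.04) with ten clusters per arm, and about 70% and 63% with five teams per arm and a team-level ICC. The gap between those pairs comes from the unstated cluster structure and should not be attributed to retention. The retention point is modest in size but worth correcting, because these are the figures on which the plan's power rests.

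**What to change.** Use one 12-month retention figure throughout. Recompute and restate the six powers at 392 completers (about 39 per team). State beside them the number of randomised clusters per arm, the number of PCPs per team, the level at which each ICC applies, alpha and sidedness. If the 15% missing case is kept, label it as an optimistic scenario and show it next to the planned case.

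The cost is a recalculation and a change of wording. Enrolment and analysis need not change for this point. The retention change makes the stated powers slightly less favourable; stating the cluster structure may move them further.

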We developed a primary care-based intervention called Peer Assisted Lifestyle (PAL) to facilitate delivery of 5As weight management counseling within primary care and increase adoption of intensive VA programs such as MOVE!. The PAL intervention uses a software tool (that we developed) delivered on tablets to facilitate 5As-based weight management counseling with a Veteran health coach and VA PACT healthcare team to promote goal-setting, behavior change, and weight loss in the primary care setting. The PAL intervention also includes up to 12 health coaching calls to patients over 1 year.

As part of a clustered randomized control trial, we will randomize up to 17 PACT teams to either Enhanced Usual Care or the PAL Intervention, recruiting up to 520 subjects.

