To improve counseling opportunities and enhance care coordination during a primary care visit, the VA adopted a patient centered medical home model called Patient Aligned Care Teams (PACT) in 2010. The PACT model provides a team-based, patient-centered approach to health care that utilizes a multidisciplinary practice team that includes a RN Care Manager, a Clinical Associate (LPN), and Administrative Associate, and the primary care provider (the "teamlet") as well as social workers, dietitians, and specialists (other team members) to deliver patient-centered care. This recent implementation of PACT provides the opportunity for longitudinal, team-based care that is integrated with the MOVE! program. However, in the 2013 MOVE! progress report, the majority (55%) of VA sites surveyed reported that MOVE! programs were separate from PACT. Improving weight management counseling by PACT teamlets could increase patient motivation to attend the MOVE! program and facilitate weight loss for those who do not attend.

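### The stated 85%/81% power for 2.2 kg does not follow from the plan's own inputs: about 72%/64% as labelled, and 75–83% for 17 randomised providers

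*Combined protocol and SAP*

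**What the plan says.** The final Sample Size and Power Analysis has two paragraphs; the first also appears under Data Analysis.

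- **First paragraph.** It assumes 5 teams per arm, 52 Veterans recruited per team and 392 completers. Its ICCs are "0.05 for Veterans within each PCP and an ICC of 0.01 for PCPs within each PACT team". It gives no power percentage for weight.
- **Second paragraph.** It changes the retention and the ICC: "If we assume the missing rate at 12 months is 15%, then we will have 44 evaluable Veterans per team", with an ICC of "0.03-0.04 for Veterans within each PACT team and an ICC of 0.01 for PCPs within each team". It then states "If the ICC of Veterans within each PACT team is 0.03, the power is 85% to detect a 2.2kg (SD=6.0kg) difference in weight", 87% for waist (2.9 cm, SD 7.7 cm) and 91% for the "hypothesized difference between 25% Veterans in the intervention arm and 10% of Veterans in the control arm". It continues: "If the ICC of Veterans within each PACT is 0.04, the powers are 81%, 83%, and 87% to detect the same effect sizes".

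The design sections describe other clusters. Specific Aims says "we will randomize up to 17 PACT teams to either Enhanced Usual Care or the PAL Intervention, recruiting up to 520 subjects". Project Methods and Study Arms/Randomization put the randomisation at provider level. The recruitment text expects 75% retention. Aim 1a hypothesises 27% versus 12% for at least 5% weight loss, not 25% versus 10%.

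**The concern.** In a cluster trial, power depends mainly on how many clusters there are, how large they are, and the level to which the ICC belongs. Here the ICC is labelled as within team, the calculation has 10 teams, and randomisation is of up to 17 PACTs at provider level. The number of PCPs per team is missing, so the role of the 0.01 cannot be determined.

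The figure concerns the primary outcome, mean weight loss at 12 months. If true power is lower, a null result is weaker evidence against a 2.2 kg effect than the plan implies, and a reader cannot reproduce the stated figure. The estimand, the analysis and the type I error are not affected.

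**Working it through.** **Inputs.** From the second paragraph: 2.2 kg, SD 6.0 kg, 5 teams per arm, 44 evaluable per team (220 per arm), ICC 0.03 or 0.04. Assumed: two-sided 0.05, equal clusters, normal approximation unless noted.

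**Formula.** Power = Φ(2.2 / (6·√(2·DE/n)) − 1.96), where n is per arm and DE is the design effect.

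**1. The plan's figure, as labelled (team level).** DE = 1 + 43·ICC.

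- ICC 0.03: DE = 2.29, SE = 6·√(2·2.29/220) = 0.866, ratio 2.541, power 72.0%.
- ICC 0.04: DE = 2.72, SE = 0.943, ratio 2.332, power 64.5%.

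| Outcome | Stated (0.03/0.04) | Recomputed |
|---|---|---|
| Weight | 85% / 81% | 72% / 64.5% |
| Waist | 87% / 83% | 74% / 67% |
| 25% vs 10% | 91% / 87% | 79–80% / 71–73% |

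The ranges in the last row cover pooled and unpooled variance. A one-sided 0.05 test would give 81.5%/75.4% for weight, still short. A t reference with 8 df gives 61%/54%.

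**2. Does the 0.01 help at team level?** If it is already part of the team correlation, nothing changes. If it is added on top, with k PCPs per team and m = 44/k, DE = 1 + (m−1)(ICC+0.01) + m(k−1)·ICC. For k = 2 to 4, power is 68–70% at ICC 0.03 and 61–63% at 0.04, which is lower.

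**3. What reproduces the stated figures?** Move 0.03/0.04 to the PCP level, so that DE = 1 + (m−1)·ICC + m(k−1)·0.01.

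| PCPs per team (assumed) | DE | Weight power |
|---|---|---|
| 2, without the 0.01 | 1.63 / 1.84 | 85% / 81% |
| 2, with the 0.01 | 1.85 / 2.06 | 81% / 76% |
| 3, with the 0.01 | 1.70 / 1.84 | 84% / 81% |
| 4, with the 0.01 | 1.63 / 1.73 | 85% / 83% |

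Two PCPs without the 0.01 also give 87.2%/83.0% for waist and 90.5%/86.7% for 25% versus 10% (pooled variance), so all six stated powers are matched to rounding. Three PCPs with the 0.01 come within about 2 points on all six.

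The documents do not settle the count. The PACT section lists "a RN Care Manager, a Clinical Associate (LPN), and Administrative Associate, and the primary care provider", which is one PCP per teamlet. The Design section cites an earlier study with 52 PCPs and 18 RN care managers, about 2.9 each. Ten teams with two or three PCPs would be 20 or 30 providers.

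**4. The design as randomised.** Read the 17 units as 17 equal provider clusters, with the second paragraph's ICCs applied to providers.

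- 15% missing: 520·0.85 = 442, so m = 442/17 = 26 and n = 221. DE = 1 + 25·ICC = 1.75 / 2.00.
- 392 completers: m = 392/17 = 23.06 and n = 196. DE = 1 + 22.06·ICC = 1.662 / 1.882, and 2.103 at ICC 0.05.

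| Completers | ICC | Power, normal | Power, t with 15 df |
|---|---|---|---|
| 442 | 0.03 / 0.04 | 83% / 78% | 78% / 72% |
| 392 | 0.03 / 0.04 | 80% / 75% | 75% / 70% |
| 392 | 0.05 (first paragraph) | 71% | 65% |

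Detectable difference at 80% power with 392 completers = 2.80·6·√(2·DE/196): 2.19, 2.33 and 2.46 kg at ICC 0.03, 0.04 and 0.05. With 15 df these are 2.34, 2.49 and 2.63 kg.

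**The case against.** The best defence is that the ICC is merely mislabelled. An ICC for PCPs within a team implies several PCPs, and the first paragraph places its Veteran ICC within PCP. With two PCPs per team and no 0.01, all six stated powers match, so the arithmetic was probably sound for some structure. This is persuasive as to how the numbers arose. It does not make them right for this plan: it needs a PCP count found nowhere in the documents, contradicts the written label, drops the stated 0.01, and implies 20 providers, not 17.

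Second, the gap for 17 providers is small on the paragraph's own 15% missing: about 2 points at ICC 0.03 and 3 at 0.04. That stands. Roughly half of the 5–6 point shortfall at 392 completers comes from the plan's two retention figures, not from clustering. Seventeen providers with all 520 Veterans evaluable would give 86%/81%, but this ignores the missing data the paragraph itself assumes.

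Third, the 17-provider figures rest on assumptions too: that 17 PACTs means 17 equal provider clusters, and that an ICC labelled within team applies to providers. The only ICC the documents label as within PCP is 0.05, which lowers power further. The documents prescribe no cluster degrees of freedom, so the 15 df values are a caution, not a correction. The planned confidence intervals will also inform a reader of a null result more directly than planned power.

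**Conclusion.** The point holds. On the inputs as labelled, the stated powers are overstated by about 13 and 16.5 points for weight and by 11–16 points for the other two outcomes. The likely source is an undocumented or mislabelled cluster level, not a slip in calculation.

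The practical shortfall is smaller. At 392 completers, the chance of missing a true 2.2 kg effect is about 20–25%, or 25–30% with 15 df, against an implied 15–19%. This rests on two-sided 0.05, equal clusters, 17 providers and an ICC of 0.03–0.04 at provider level. The failure to reproduce the figure as labelled does not depend on how the 17 units are read. It should be fixed, but it does not threaten the validity of the trial.

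**What to change.** Replace the power text in both places with one calculation for the design as randomised. It should state:

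- alpha and sidedness;
- the cluster unit, the number of clusters and their size;
- the level of each ICC, and the PCPs per team if a team level is kept;
- one retention figure (75% or 85%);
- one pair of rates for at least 5% weight loss (27% vs 12%, or 25% vs 10%).

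Restate power for 2.2 kg. On the reading used here it is about 75–80% at ICC 0.03–0.04 with 392 completers (70–75% with 15 df), with ICC 0.05 as a sensitivity value (71%; 65% with 15 df). Report the detectable difference, about 2.2–2.5 kg (2.3–2.6 kg with 15 df). If 85%/81% came from a PCP-level ICC, say so and give the PCP count used.

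The cost is a change of wording and a less favourable stated power, with no extra enrolment and no change to the analysis.
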